#### 4.2.3 Analysis Visit Windows

The efficacy measures of fasting lipid panel (TG, APOC-III, VLDL-C, remnant cholesterol, TC, non-HDL-C, apoB, HDL-C, LDL-C, and ApoA-1), including the data from both scheduled and unscheduled visits, will be mapped to analysis visits according to the visit windows in [Table 1](#) below.

The intent of these visit windows is not to align with those prescribed for visit scheduling in the study protocol, but rather based on the protocol-defined target study day, to delineate mutually exclusive windows so that all efficacy assessments proximal to a particular study week can be integrated to best represent the patient's status during that period of the study. Visits after Week 53 are part of the post-treatment assessment period and will be summarized by the visit label provided in the data. No visit windows are needed for the data of post-treatment visits.

For lipid data, local lab data will not be used unless central lab assessments are not available at certain visit. When calculating the baseline and analysis endpoints, only if the data from central lab is missing, then the local lab data will be utilized. If there are multiple assessments within a visit window, the assessment nearest the target day will be used unless two assessments are equally near, in which case the average value will be used.

If a patient discontinued early from the treatment period but attended applicable landmark visits to collect efficacy assessments, then those assessments should be mapped to analysis visits and utilized in the analyses as well, unless otherwise stated.

**Table 1: Analysis Windows (Days)**

Efficacy	Nominal Visit (Week)	Target Day	Analysis Visit Window (Day)
Lipid Panel	5	29	2-43
	9	57	44-71
	13	85	72-99
	17	113	100-127
	21	141	128-155
	25	169	156-176
	27	183	177-190
	29	197	191-225
	37	253	226-281
	45	309	282-330
	51	351	331-358
	53	365	359-379 a

aDay 379 represents the middle point between the target days for the Week 53 visit and the first post-treatment assessment visit.

All other by-visit assessments will be summarized using the visit labels provided in the data. Multiple results with the same visit label will be averaged. Unscheduled results from the central lab will not be included in the by-visit summaries but will be used in the determination of baseline, laboratory abnormality summaries and shift analyses, and presented in data listings. Local lab data will be only used in platelet analyses (including by visit summary, abnormality summaries, and shift from Baseline to worst post-baseline), and presented in data listings. For other safety lab parameters, local lab data will not be included in any analyses and data summaries.

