All lab samples are to be sent to the central laboratory by overnight courier and processed. Lab alerts issued will indicate the applicable protocol section to facilitate review and will be immediately and simultaneously sent by email to the Investigator, the Sponsor and the CRO Medical Monitors, the Sponsor Drug Safety Physician, and the Clinical Trial Manager (CTM), and should be received by them within 2 days from sample collection. All lab sample results from local laboratories are received by the Study Center staff per the local laboratories' standard reporting time and should be entered as soon as possible (ideally within 1 week) into the electronic Case Report Form (eCRF) to inform the Sponsor and CRO study monitoring teams.

All PLT count results must be reviewed promptly (within 2 business days of receipt) by the Investigator, or designee, to ensure that the count has not met a dose interruption or stopping rule. Any case of PLT count reduction to levels below 50,000/mm^3 accompanied by a major bleeding (MB) event or clinically relevant non-major bleeding event (CRNMB), or PLT count of < 25,000/mm^3 independent of a MB or CRNMB event, is considered an AE of special interest (AESI) and must be reported in an expedited fashion to the Sponsor as per Section 9.3.4 and Section 9.4.1.

All liver and renal function tests must also be reviewed promptly (within 2 business days of receipt) by the Investigator, or designee, to ensure that the result has not met the stopping rule.

All lab alerts received, including those related to PLT, liver, or renal function monitoring/stopping rules, are also reviewed promptly by the Sponsor and the CRO Medical Monitors who will agree on actions to be taken according to the Medical Data Surveillance Plan.

Further information on safety monitoring and actions to be taken by the Study Investigator are provided in Section 8.5.

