## 8.5 Safety Monitoring and Permanent Stopping Rules

Please refer also to the ‘Guidance for Investigator’ section of the Investigator’s Brochure.

- For the purposes of safety monitoring and permanent stopping rules Baseline is defined as the average of the Day 1 pre-dose assessment and the last measurement prior to Day 1
- In addition to the standard monitoring of clinical safety parameters, the following guidelines are provided for the monitoring of selected parameters chosen based on preclinical and clinical observations
- In case of discrepancy between the test results from 2 sources, such as between the central and local lab, safety-mandated action must be initiated based on the more critical (lower or higher, as relevant) of the 2 values

**Confirmation Guidance:** At any time during the study (Treatment or Post-Treatment Periods), the initial clinical laboratory results meeting the safety monitoring criteria presented below **must be confirmed** by performing measurements (ideally in the same laboratory that performed the initial measurement) on new specimens. All new specimen collections should take place as soon as possible (ideally within 3 days of the initial collection).

**Re-dosing Guidance:** In the event the initial laboratory result meets a stopping criterion, the results from the retest **must be available and reviewed by a Medical Monitor** prior to administration of the next dose of Study Drug (olezarsen or placebo). In general, patients who do not meet the stopping rules based upon retest may continue dosing. However, the Investigator and the Sponsor Medical Monitor (or designee) should confer as to at which dose Study Drug should be restarted, and whether additional close monitoring of the patient is appropriate. If any of the permanently stopping criteria described below are met, the patient will be permanently discontinued from further treatment with Study Drug (olezarsen or placebo), evaluated fully as outlined below and in consultation with the Sponsor Medical Monitor or designee, and will be followed up in accordance with Section 8.8. of the protocol.

The Investigator may interrupt or permanently discontinue study treatment for any medical reason including changes in clinical laboratory results.

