### 8.5.1 Safety Monitoring and Permanent Stopping Rules for Liver Chemistry Tests

The following rules are adapted from the draft guidance for industry, “Drug-Induced Liver Injury: Premarketing Clinical Evaluation,” issued by the U.S. Department of Health and Human Services, Food and Drug Administration, July 2009. For a definition of Baseline, please refer to guidance above.

All patients will have liver chemistry tests monitored monthly during the Treatment Period. Upon completion of the study Treatment Period, liver chemistry tests should be monitored during the Post-Treatment Follow-Up Period as per visit schedule in [Appendix A](#).

All routine liver chemistry test results will be reviewed on an ongoing basis at the safety review by the Sponsor Medical Monitor.

All lab alerts for abnormal liver chemistry tests must be promptly reviewed by the Investigator (within 2 business days of receipt) and Medical Monitor(s) according to the Medical Data Surveillance Plan.

In the event of appearance of symptoms or signs of hepatic injury (jaundice, fatigue, nausea, vomiting, right upper quadrant pain or tenderness, fever, rash, abnormal bleeding or bruising, or eosinophilia  $> \text{ULN}$ ) liver enzymes (ALT/AST) and total bilirubin should be tested as soon as possible (ideally within 3 days). Testing at a lab that is local to the patient is permissible for this purpose.

In the event of an **ALT or AST measurement that is  $> 3 \times \text{ULN}$  (or the greater of  $2 \times \text{baseline value}$  or  $3 \times \text{ULN}$  if the baseline value was  $> \text{ULN}$ )** at any time during the study (Treatment or Post-Treatment Period), and the initial measurement(s) is confirmed (as described in Confirmation Guidance above) the following steps should be taken:

1. The Study Drug must be paused
2. Liver chemistry tests (ALT, AST, alkaline phosphatase [ALP], INR and total bilirubin) retested at least once weekly until ALT and AST levels become  $\leq 1.5 \times \text{ULN}$  or  $1.5 \times \text{baseline}$  if the baseline value was  $> \text{ULN}$
3. Further investigations into the cause of liver chemistry elevations should be performed. These may include the following evaluations\*:
  - a. Obtain a more detailed history of symptoms and prior and concurrent diseases

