- Quantitative assessments will be summarized using descriptive statistics in terms of observed values, change and percent change from Baseline for each laboratory parameter by scheduled study visit.
- Qualitative assessments will be summarized by frequency counts and percentages by scheduled study visit.

By-subject listings of all laboratory data will be provided based on randomized patients.

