#### **Liver enzyme elevation**

- ALT or AST  $\geq$  ULN
- ALT or AST  $\geq 3 \times$  ULN and ALT or AST  $\geq 2 \times$  baseline
- ALT/AST  $\geq 3 \times$  ULN,  $\geq 5 \times$  ULN,  $\geq 8 \times$  ULN,  $\geq 10 \times$  ULN, or  $\geq 20 \times$  ULN, for patients having elevation in liver enzymes (ALT  $\geq 3 \times$  ULN), the time to onset of the first event will be summarized using descriptive statistics
- Total bilirubin  $\geq 2 \times$  ULN,  $\geq 5 \times$  ULN,  $\geq 8 \times$  ULN
- Direct bilirubin  $\geq 2 \times$  ULN,  $\geq 5 \times$  ULN

- Highest post-baseline value of ALT/AST fall in:  $\geq 3 \times \text{ULN}$  -  $< 5 \times \text{ULN}$ ,  $\text{ALT} \geq 5 \times \text{ULN}$  -  $< 10 \times \text{ULN}$ ,  $\text{ALT} \geq 10 \times \text{ULN}$  -  $< 20 \times \text{ULN}$  (the risk difference will not be provided for this category)
- $\text{ALT or AST} \geq 3 \times \text{ULN}$  and  $\text{Total bilirubin} \geq 2 \times \text{ULN}$
- $\text{GGT} \geq 2 \times \text{ULN}$
- $\text{ALP} \geq 2 \times \text{ULN}$
- $\text{ALP} \geq 3 \times \text{ULN}$
- $\text{ALP} \geq 2 \times \text{ULN}$  and ( $\text{Baseline ALP} < 2 \times \text{ULN}$  or  $\text{Baseline ALP}$  missing)
- $\text{ALT or AST} \geq 3 \times \text{ULN}$  (or the greater of  $2 \times \text{baseline value}$  or  $3 \times \text{ULN}$  if the baseline value was  $\geq \text{ULN}$ ) and  $\text{Total bilirubin} \geq 2 \times \text{ULN}$  and  $\text{ALP} \geq 2 \times \text{ULN}$
- $\text{ALT/AST} \geq 3 \times \text{ULN}$  and  $\text{INR} \geq 1.5$
- $\text{INR} \geq 1.5 \times \text{ULN}$
- $\text{INR} \geq 3 \times \text{ULN}$
- $\text{INR} \geq 5 \times \text{ULN}$

The number and percent of patients falling in each of the following categories based on confirmed post-baseline results will be tabulated by treatment group and total olezarsen treated. A confirmed value is based on a consecutive lab value performed on a different day to, but within 10 days of, the initial value. If that value is in the same or worse category, then the initial value is confirmed. If the consecutive value is in a better category, then the initial value is confirmed using the consecutive value category. If there is no retest within 10 days, then the initial value is presumed confirmed. If there are multiple results on the same day, then the worst value will be utilized in the analysis.

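### The SAP keeps local liver and renal results out of every analysis, so local-only peaks go uncounted and some ALT/AST elevations refuted only by a local retest count as confirmed

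*Combined protocol and SAP*

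**What the plan says.** **SAP 4.2.3, text after Table 1.** "Local lab data will be only used in platelet analyses"; for everything else in the safety laboratory, "For other safety lab parameters, local lab data will not be included in any analyses and data summaries". That covers ALT, AST, ALP, bilirubin, INR, creatinine, eGFR, UPCR and UACR. The same paragraph does bring unscheduled central results into the abnormality and shift analyses.

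**SAP 4.10.3.2, liver.** A confirmed value needs a consecutive value on another day within 10 days. The default is: "If there is no retest within 10 days, then the initial value is presumed confirmed".

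**SAP 4.10.3.2, renal.** Threshold counts use any value after first dose, and separately the final visit. They have no confirmed category.

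**Protocol 8.5.** The same laboratory is preferred for a confirmatory sample but not required. Where two sources disagree, "safety-mandated action must be initiated based on the more critical (lower or higher, as relevant) of the 2 values".

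**Protocol 8.5.1 and 8.5.2.** Symptoms of possible hepatic or renal injury call for prompt testing: "Testing at a lab that is local to the patient is permissible for this purpose".

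**Protocol 6.2.1.** Local results are recorded by the site in the electronic database and eCRF.

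**The concern.** The protocol treats a local liver or renal result as real safety information, and a pause or stop of study drug can rest on it. The SAP then analyses the liver and renal laboratory data as if that result did not exist.

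Two kinds of error are possible, in opposite directions. A symptomatic patient tested near home may have the true peak recorded only locally, and that peak is not counted. Conversely, a central ALT or AST elevation that a local retest shows to be transient may be counted as confirmed, because the retest is discarded and the patient then looks untested.

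At stake are the liver and renal laboratory tables for each dose, where counts may be small. Protocol 2.3.4 reports that no patient met a liver monitoring rule in the earlier 114-patient Phase 2 study, whose highest dose was 50 mg every 4 weeks. INR is the most exposed analyte: the protocol's Schedule of Procedures has only two routine post-baseline draws, at Weeks 25 and 53. The combined ALT/AST-with-INR categories therefore lean on unscheduled samples.

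**Working it through.** The plan states no figure for this point, so there is none to reproduce. The check applies the SAP rules as written to constructed ALT sequences and then works out the weight of one patient.

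**Step 1: the liver rule.** For each value at or above 3 × ULN, take the next value on a different day within 10 days. If there is none, the initial value is confirmed by default. If there is one, it decides. Apply this once to central values only (the SAP) and once to central and local values together. The sequences below are assumptions in multiples of ULN, chosen to show the logic.

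| Case | SAP: any ≥ 3 / confirmed ≥ 3 | With local: any ≥ 3 / confirmed ≥ 3 |
|---|---|---|
| A: central 3.4 day 0, local 1.2 day 3, central 1.1 day 28 | yes / **yes** | yes / **no** |
| B: as A, but the next central 1.1 falls on day 8 | yes / no | yes / no |
| C: central 1.0 day 0, local 9 days 10 and 12, central 1.4 day 28 | **no / no** | **yes / yes** |
| D: central 1.0 day 0, local 9 day 10, central 8.5 day 12 | yes / yes | yes / yes |

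Case A is the false confirmation. It needs all three of a central elevation, a refuting local retest, and no central retest within 10 days. Case C is the omission. Cases B and D show that neither error arises when a central sample in the window tells the same story.

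**Step 2: which outputs are touched.**

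- *Omission, liver:* the single-value, confirmed and combined (bilirubin, INR) categories, the eDISH plots, and the ALT, AST and bilirubin worst-value shifts.
- *Omission, renal:* the creatinine, eGFR, UPCR and UACR threshold counts, and the creatinine worst-value shift.
- *False confirmation:* only the outputs built on confirmed ALT or AST. The single-value counts and eDISH peaks already include the central value.
- *Renal threshold tables:* no confirmation rule, so only the omission applies.
- *Platelets:* neither error, because local data are used.

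**Step 3: weight of one patient.** Planned enrolment is 152, randomised 1:1 to cohorts and 3:1 within each (Protocol 3.1).

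- Olezarsen per dose: 152/2 × 3/4 = 57. Pooled placebo: 152 × 1/4 = 38. Pooled olezarsen: 57 + 57 = 114.
- One reclassified patient: 1/57 = 1.8%; 1/38 = 2.6%; 1/114 = 0.9%.

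These use planned arm sizes and assume every patient has a post-baseline value. The number of local-only tests is not in the documents, so the step from one patient to an expected bias cannot be made.

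**The case against.** **The values are not lost.** The SAP says of local data, in a sentence that starts with platelets, "shift from Baseline to worst post-baseline), and presented in data listings", and section 4.10.3.1 adds: "By-subject listings of all laboratory data will be provided based on randomized patients". Under Protocol 9.3.1 a laboratory deterioration with symptoms, or one that changes study treatment, is an adverse event, and under 9.3.3 hospitalisation makes it serious. Such cases can enter the hepatic and acute kidney injury event tables (SAP 4.10.2.5.4 and 4.10.2.5.5) and the interruption and discontinuation counts. This stands. A reader might infer that severe local values disappear from the report altogether, or that no output would reflect the dosing action; the documents do not support either. But listings and coded events do not replace threshold counts by arm or an eDISH plot.

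**False confirmation is narrow and errs towards caution.** The protocol prefers the same laboratory for confirmation, and discretionary local testing under 6.2.1 is additional to central samples. The error over-counts hepatic signals. This also stands, and it limits frequency. It does not make the classification right: Protocol 8.5.1 presumes confirmation, for permanent stopping, when a retest was not done or is missing, whereas here a retest exists.

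**Central-only analysis is a legitimate choice.** It keeps one assay and one set of reference ranges. Platelets are a special case because samples clump and the protocol's platelet panel places the EDTA platelet sample at the local laboratory. This is a fair reason to keep the main tables central. It is not a reason to have no supplementary output, or to treat a recorded retest as absent.

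**Conclusion.** The point holds in two parts. For liver and renal tests, a severe value seen only at a local laboratory is not counted in the abnormality outputs or, where applicable, the worst-value shift and eDISH outputs. For ALT and AST alone, a central elevation refuted solely by a local retest, with no central retest within 10 days, is counted as confirmed.

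A reader might extend the second part to renal alerts. The 10-day presumption sits only in the liver part of SAP 4.10.3.2. SAP 4.10.2.5.4 does tabulate patients meeting the renal monitoring and stopping criteria, but it does not say how confirmation is derived there, so the presumption cannot be read into it. A reader might also infer that one missed value would erase the whole hepatic signal. The documents give no expected number of such cases, so that cannot be shown.

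The size is 1.8 percentage points per patient in a dose arm and 2.6 in pooled placebo, at planned numbers. The total effect is unknown. The conclusion assumes that SAP 4.2.3 is applied as written and that some local-only testing occurs. This is a cheap improvement.

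**What to change.** 1. **Confirmation rule (SAP 4.10.3.2).** State that a local ALT or AST result on a different day within 10 days counts as the retest, expressed as a multiple of the reporting laboratory's own ULN. Keep the present order: the next value in time decides, and the worst value is used if several fall on one day. Add this as an exception in SAP 4.2.3.
2. **Supplementary outputs.** Repeat the liver and renal abnormality counts, the worst-value shifts and the eDISH plots with local values included, and label them as sensitivity outputs. Leave the main tables, apart from the confirmation rule in item 1, and all by-visit means on central data.
3. **Limits to state.** List and count local results that have no usable reference range or unit. Note that a local creatinine is compared with a central baseline, so ratios to baseline mix assays.

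The cost is a short SAP revision, some programming, and obtaining and mapping local reference ranges, which the documents do not say are collected. No extra patient testing is needed, and the protocol's dosing rules are untouched. The wording should be settled before unblinding.

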### 4.3 Software

All report outputs will be produced using SAS® version 9.4 or a later version in a secure and validated environment.

### 4.4 Study Subjects

#### 4.4.1 Disposition of Subjects

Subject disposition will be summarized based on all screened subjects. The summary will include the following information:

- The total number of subjects who were screened, screen failed, randomized, and the major reason of screen failure will be summarized for all screened subjects. The number and percentage of screen failures due to COVID-19 impact will also be summarized.
- The number and percentage of subjects randomized, treated, completed study treatment, early terminated from study treatment, major reasons for early termination of study treatment, completed post-treatment follow-up, early terminated from post-treatment follow-up, major reasons for early termination of post-treatment follow-up, will be presented by treatment group, total olezarsen treated, and overall based on

randomized subjects. The number and percentage of subjects who discontinued treatment or post-treatment follow-up related to COVID-19 will also be summarized.

A by-subject listing of disposition data for randomized subjects will be provided. A separate disposition listing including eligibility criteria for screen failures will also be provided.

#### 4.4.2 Protocol Deviations

Protocol deviations will be recorded in the eCRF, where they will be classified as “minor” or “major”. All protocol deviations and major protocol deviations will be summarized by deviation category, by treatment group, total olezarsen treated, and overall, based on randomized subjects. The number and percentage of subjects with protocol derivation, in each deviation category and due to COVID-19 related impact will be provided for all protocol deviations or major protocol deviations in separate tables. All protocol deviations will be listed.

Significant protocol deviations are defined as those deviations from the protocol likely to impact the perceived efficacy and/or safety of study treatments. The impact of significant protocol deviations on the efficacy and/or safety results will be investigated by assessing the robustness of the study results and conclusions to the choice of analysis set, both including and excluding data potentially affected by significant protocol deviations. Before unblinding, the data will be reviewed by the clinical group for identification of significant protocol deviations.

### 4.5 Demographic and Baseline Characteristics

Demographic data and baseline characteristics will be summarized by treatment group, total olezarsen treated, and overall using descriptive statistics based on the FAS, PPS, and Safety Set, separately.

Demographic data include, but are not limited to age, age group (< 65 years, ≥ 65 years), sex, ethnicity, race, height, weight, and body mass index (BMI).

Key baseline laboratory parameters include baseline HbA1c and baseline lipids profile: fasting TG, apoC-III, TC, HDL-C, apoB, remnant cholesterol, VLDL-C, non-HDL-C, LDL-C and apoA-1.

A by-subject listing of the demographic data and the baseline characteristics will be provided for randomized subjects.

